8.5 Description of Statistical Analyses

8.5.1 General Considerations

All analyses of all endpoints except the primary analysis, will be performed exploratively and, differences with a p-value of 0.05 or less will be considered nominally statistically significant.

Parameter estimates with associated 95% confidence intervals (CIs) will be reported in each analysis. No correction for multiple testing will be applied for any secondary or tertiary analysis.

Subjects' demographic factors and baseline clinical characteristics will be summarized with the following measures: mean with standard deviation, minimum and maximum for normally distributed continuous variables, median with interquartile range, minimum and maximum for other continuous variables and counts with percentages for categorical variables.

As the secondary and tertiary analysis set concerns repeated measurements of outcomes for each individual, it is likely that observations pertaining to each individual will be correlated. Furthermore, as this is a multi-center trial, it is likely that clustering of individuals within trial sites will produce an additional source of correlation. Mixed-effects regression, whereby a three-level hierarchical model is specified for observations within subjects within trial sites, will be used to account for within-subject and within-center correlation (Gibbons, 2010).

The parametric assumptions underlining the regression models specified will be examined. Should these assumptions be violated, alternative methods, such as non-parametric approaches, may be considered in addition.

Assessment Schedules

It is likely that the second year treatment may be delayed substantially due to grade 3 or 4 lymphopenia for a small number of subjects for whom the second dose is not required immediately. Due to the need for a finite follow-up period, a buffer of 3 months is given for subjects who do not receive the second treatment at the specified time. Subjects for whom treatment is delayed by over 3 months may not have all assessment data captured and as such, these observations will be treated as missing in efficacy analyses.

In each analysis, should assessment be delayed, subjects' assessment data will be treated as though it occurred at the time point specified and inferences will be conducted accordingly.

Missing Data

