8.2 Definition of Analysis Sets and Subgroups

Enrolled Set (ES)

All subjects enrolled in the study, i.e., all subjects with a signed informed consent.

Intent-to-treat Set (ITT)

All subjects classified as eligible (i.e., medication assigned by iRT at the Baseline Visit).

Full Analysis Set (FAS)

All subjects in the ITT treated with at least one dose of study medication.

Treatment Completer Set – Year 1 (TCS-1)

All subjects from the FAS who completed the full Treatment Course of the first year (Treatment Course 1). Subjects will be classified as Treatment Completer for the first year if they have a compliance greater than or equal to 100% for Treatment Course 1.

Treatment Completer Set – Year 2 (TCS-2)

All subjects from the FAS who completed the full Treatment Course of the first and the second year. Subjects will be classified as Treatment Completer for the second year if they have a compliance greater than or equal to 100% for Treatment Course 1 and Treatment Course 2 and received the treatment without delay (see Section 9 for definition).

Safety Analysis Set (SAF)

All subjects treated with at least one dose of study medication.

Unless otherwise specified, all efficacy analyses will be performed on the FAS.

Some tertiary analyses will be repeated on the Treatment Completer Sets and the primary analysis, on the ITT (if different from FAS), to evaluate the robustness of the primary results to deviations of the planned treatment regimen. Further details are given in the respective sections. All safety analyses will be performed on the SAF.

Additional Subgroup or Subset Analysis Sets

Subgroup analyses will be performed on subgroups as defined below.

- High-relapse activity (HRA)
 - HRA: at least 2 relapses in the previous year (i.e. the number of historical relapses within 12 months prior to Baseline ≥ 2) regardless of prior use of DMDs
 - Non-HRA: otherwise

Unless otherwise indicated, all descriptive statistical analyses will be presented separately for the HRA subgroups.

- Previous treatment with Disease Modifying Drugs (DMDs):
 - DMD pre-treated: Subjects will be categorized as DMD pre-treated if they have taken DMDs any time before start of study medication. Details of the definition of DMDs are specified in Appendix 1 (Section 18.1).
 - Pre-treatment naïve: all subjects not classified as DMD pre-treated.

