The primary analysis and selected demographic and background characteristics as well as selected tertiary analyses will be repeated for these subgroups.

The following subset(s) are defined:

- Baseline Period CUA count > 0 (i.e. all subjects with a CUA lesion count > 0 during the Baseline Period)

As subjects with a CUA count of 0 during the Baseline Period cannot show an improvement in the number of CUA lesions during the study, some of the efficacy analyses will be repeated for this subset that has at least one CUA lesion during the Baseline Period.

9 General Specifications for Data Analyses

Treatment groups

The treatment group will be labeled as Mavenclad®.

Significance level

The three hypotheses of the primary analysis (see Section 14.1) will be tested as one -sided, on a 2.5% significance level. The testing procedure will stop as soon as one of the hypotheses cannot be rejected following a pre-specified order. Due to this sequential order of tests an adjustment for a potential type-I-error inflation due to the multiple testing is not required.

CCI [REDACTED] All statistical tests will be performed two-sided. If confidence intervals are to be calculated, these will be two-sided with a confidence probability of 95%, unless otherwise specified in this IAP.

Presentation of continuous and qualitative variables

Continuous variables will be summarized using descriptive statistics, i.e., number of subjects, number of subjects with missing and non-missing values, mean with standard deviation, median, 25th Percentile - 75th Percentile (Q1-Q3), minimum, and maximum.

Qualitative variables will be summarized by counts and percentages.

Unless otherwise stated, the calculation of proportions will be based on the number of subjects in the analysis set of interest. Therefore, counts of missing observations will be included in the denominator and presented as a separate category.

In case where the analysis refers only to certain Visits, percentages will be based on the number of subjects still present in the study at that Visit, unless otherwise specified.

Definition of Baseline

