 - and any Lymphocyte count < 800 cells/mm³ at or after Month 12 Visit and before start of Treatment Course 2.
- Before or at / after Start of COVID-19 pandemic

The cumulative dose is defined as the sum of the number of tablets taken 10 mg divided by the weight for treatment year:

Cumulative dose = number of tablets taken in Treatment Course 1 * 10mg / weight in kg at Baseline + number of tablets taken in Treatment Course 2 * 10mg / weight in kg at Month 12b Visit.

The cumulative dose will be calculated only if the weight and number of tablets are available. Otherwise it will be missing. If the Treatment Course 2 wasn't started (i.e. no tablet taken in Treatment Course 2), the cumulative dose will be calculated only for the Treatment Course 1.

A subject data listing of the treatment compliance will be provided for the SAF.

14 Efficacy Analyses

The following sections describe the planned analyses for each of efficacy endpoints.

For the detailed definition of covariates and stratification factors that are used in the statistical models see Section 9. Details about the derived MRI endpoints and general handling of MRI data is described in Section 9 (“Data Handling of MRI data”).

Descriptive summary statistics will be presented for the absolute values and the changes from Baseline as applicable by Visit [Protocol Scheduled Visits except for Baseline (defined in Section 9)], or Period, for all efficacy endpoints (and the components, where applicable) for the FAS and respective subgroups or subsets for which the variables are analyzed. Details about the presentation of continuous and categorical variables are given in Section 9.

Wherever possible, all estimated results from the statistical models will be calculated with the same observed margin which reflects the population of the whole corresponding analysis set, regardless of missing data.

14.1 Primary Endpoints: Differences in the counts of CUA MRI lesions during the first 6 months compared to Baseline

The primary endpoints for the trial are defined as the differences in counts of CUA MRI lesions during the first 6 months compared to Baseline, i.e., the following differences will be evaluated:

1. Period of Month 1 to Month 6 compared to the Baseline Period.
2. Period of Month 2 to Month 6 compared to the Baseline Period.
3. Period of Month 3 to Month 6 compared to the Baseline Period.

For the detailed definition of Periods, please see Section 9 “Data Handling of MRI data”.

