1. H_{03}
2. H_{02}
3. H_{01}

The three hypotheses will be tested one-sided on a 2.5% significance level. The testing procedure will stop as soon as one of the hypotheses cannot be rejected following the pre-specified order. Due to this sequential order of tests an adjustment for a potential type-I-error inflation due to the multiple testing is not required.

An estimate for the difference in CUA lesions during the specified Periods compared to the Baseline Period will be reported, together with one-sided p-values. In addition, 95% CI and 2-sided p-values will be presented to allow for comparison with the 2-sided secondary and tertiary analyses.

The LS Means will be calculated with observed margin which reflects the distribution of age, EDSS categories at Baseline and respective Baseline Period CUA Lesion of the FAS. An unstructured covariance matrix will be assumed for the model. If the model doesn't converge a variance components covariance structure will be used instead or the results of sensitivity analysis with center effect as a fixed effect will be used instead.

Analysis (Analysis Set)	Derivation	Statistical Analysis Methods	Missing data handling
Primary endpoints: Differences in the counts of CUA MRI lesions during the first 6 months (i.e., during Periods months 1-6, 2-6, 3-6) compared to Baseline (i.e., the Period from Screening to Baseline) ^(a)			

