Primary (FAS)	
 1. Period 3 (Month 3-6): $\Delta\text{CUA}(p_3)$ (Hypothesis 3) 2. Period 2 (Month 2-6): $\Delta\text{CUA}(p_2)$ (Hypothesis 2) 3. Period 1 (Month 1-6): $\Delta\text{CUA}(p_1)$ (Hypothesis 1) 	
P-values for the three Hypotheses from the Wilcoxon signed-rank test will be presented. The testing procedure will stop as soon as one of the hypotheses cannot be rejected following the pre-specified order (H3, H2, H1). Due to this sequential order of tests an adjustment for a potential type-I-error inflation due to the multiple testing is not required.
 
The Wilcoxon signed-rank test will be complemented by the estimated Least Square Means (LS Means) and corresponding Standard Errors (SE) including one-sided p-values as well as two-sided p-value and 95% CIs from the mixed-effects linear model with the following adjusting factors:
 
 • Baseline score, • Age (in years), • EDSS at Baseline (≤ 3, >3), • Within-pooled center correlation. 
In addition, the distribution of $\text{CUA}(p_i)$ and $\Delta\text{CUA}(p_i)$ will be displayed graphically using box plots.
	
Missing observations: Subjects with a missing CUA lesion count at either the Baseline Period or the respective post-Baseline Period will not be included in the analysis.

$\Delta\text{CUA}(p_i)$ = Difference in the standardized CUA lesion count between Period i and the Baseline Period (a) 6-month interim analysis
			

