14.1.2 Primary Objective: Sensitivity Analyses of the primary endpoints

The robustness of the results of the primary analysis will be evaluated by the following

- Multiple Imputation to handle missing data using different assumptions,
- Non-parametric factorial model for longitudinal data,
- Generalized model assuming negative binomial distribution,
- Mixed-effects linear model with pooled-centers as fixed effects.

To evaluate further the impact of the potential zero inflation, the primary endpoint will be classified in different response categories for each Period as follows:

- Presence of MRI activity
 - Yes (CUA lesion count > 0)
 - No (CUA lesion count = 0)
- Standardized CUA lesion count classified to:
 - 0 (standardized CUA lesion count = 0)
 - >0 – 1 (standardized CUA lesion count > 0 and less or equal to 1)
 - >1 (standardized CUA lesion count > 1)

Analysis (Analysis Set)	Derivation	Statistical Analysis Methods	Missing data handling
Primary endpoints: Differences in the counts of CUA MRI lesions during the first 6 months (i.e., during Periods months 1-6, 2-6, 3-6) compared to Baseline Period (i.e., the Period from Screening to Baseline) (a).			
Sensitivity (FAS by subgroup "High-relapse activity")	Period 3 (Month 3-6): $\Delta\text{CUA}(p_3)$	Same as in the Primary Analysis (see Section 14.1.1)	Same as in the Primary Analysis (see Section 14.1.1)
	Period 2 (Month 2-6): $\Delta\text{CUA}(p_2)$		
	Period 1 (Month 1-6): $\Delta\text{CUA}(p_1)$		
Sensitivity (FAS by subgroup "Previous treatment with DMDs")	Period 3 (Month 3-6): $\Delta\text{CUA}(p_3)$		
	Period 2 (Month 2-6): $\Delta\text{CUA}(p_2)$		
	Period 1 (Month 1-6): $\Delta\text{CUA}(p_1)$		
Sensitivity (FAS for subset "Baseline Period CUA count > 0")	Period 3 (Month 3-6): $\Delta\text{CUA}(p_3)$		
	Period 2 (Month 2-6): $\Delta\text{CUA}(p_2)$		
	Period 1 (Month 1-6): $\Delta\text{CUA}(p_1)$		
Sensitivity (FAS)	Period 3 (Month 3-6): $\Delta\text{CUA}(p_3)$	Same as in the Primary Analysis (see Section 14.1.1)	Multiple Imputation (see below for details)
	Period 2 (Month 2-6): $\Delta\text{CUA}(p_2)$		
	Period 1 (Month 1-6): $\Delta\text{CUA}(p_1)$		
Sensitivity (FAS)	Period 3 (Month 3-6): $\Delta\text{CUA}(p_3)$	Non-parametric factorial model for longitudinal data. Fixed factors: 
 • Age in years ($\leq 40, 40 < 65$), • EDSS at Baseline ($\leq 3, > 3$), (see below for details)	Same as in the Primary Analysis (see Section 14.1.1).

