14.3.7 Active T2 lesion count

The number and changes from Baseline of the different types of active T2 lesions will be presented by Period or Visit.

Active T2 lesion count will be further classified as follows for each Visit:

- Active T2 lesion count > 0
 - Yes (Active T2 lesion count > 0)
 - No (Active T2 lesion count = 0)

Analysis (Analysis Set)	Derivation	Statistical Analysis Methods	Missing data handling
Tertiary endpoint: Changes in the standardized total active T2 lesion count (without T1 Gd+) during pre-defined post-Baseline Periods compared to the Baseline Period^(a)			
Tertiary (FAS)	Change from Baseline of the standardized total active T2 lesion count without T1 Gd+ to Periods 1-3.	Descriptive summary statistics.	
Tertiary endpoint: Changes in standardized total active T2 lesion count during pre-defined post-Baseline Periods compared to the Baseline Period (i.e., the Period from Screening to Baseline)^(a)			
Tertiary (FAS)	Period 3 (Month 3-6): $\Delta T2(p3)$	Same as in the Primary Analysis (see Section 14.1.1)	Same as in the Primary Analysis (see Section 14.1.1)
Tertiary (FAS by subgroup "High-relapse activity")			
Tertiary (FAS by subgroup "Previous treatment with DMDs")	Period 2 (Month 2-6): $\Delta T2(p2)$		
Tertiary (FAS for subset "Baseline Period CUA count > 0")	Period 1 (Month 1-6): $\Delta T2(p1)$		
Tertiary endpoint: Total active T2 Lesion count by Visit^(a)			
Tertiary (FAS)	Change from Baseline in total active T2 Lesion count at Month i Visit, where i=2, 3, 6.	Same as in the Tertiary Analysis of Change from Baseline in T1 Gd+ lesion count (see Section 14.3.3)	Same as in the Tertiary Analysis of Change from Baseline in T1 Gd+ lesion count (see Section 14.3.3)
Tertiary (FAS by subgroup "High-relapse activity")			
Tertiary (FAS by subgroup "Previous treatment with DMDs")			
Tertiary (FAS for subset "Baseline Period CUA count > 0")			
Tertiary endpoints: Change from the Baseline Period in Annualized Active T2 lesion count to the six months post-Baseline Periods			
Tertiary (FAS)	Period 6.1 (Baseline-Month 6): $\Delta T2(p_{6.1})$	Mixed-effects linear model for repeated measures, same as in Tertiary Analysis for Change from Baseline in CUA lesion count (see Section 14.3.1)	Same as in Tertiary Analysis for Change from Baseline in CUA lesion count (see Section 14.3.1)
Tertiary (FAS by subgroup "High-relapse activity")	Period 6.2 (Month 6-12): $\Delta T2(p_{6.2})$		

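### The Baseline Period CUA > 0 subset is selected on its own comparator, so its signed-rank p-values do not hold 2.5% as evidence of a drug effect, and its LS-mean margin is unclear

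*SAP*

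**What the plan says.** The primary differences in SAP 14.1.1 are the standardized CUA count in Period 3, 2 or 1 minus the Baseline Period count. They are tested in that order by one-sided Wilcoxon signed-rank tests at 2.5%.

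SAP 8.2, under "Additional Subgroup or Subset Analysis Sets", defines a subset with a Baseline Period CUA count above zero. Its reason is that subjects at zero have no room to improve, and so "some of the efficacy analyses will be repeated for this subset that has at least one CUA lesion during the Baseline Period". The sensitivity table in SAP 14.1.2 lists "FAS for subset 'Baseline Period CUA count > 0" for Periods 3, 2 and 1, with the same methods as the primary analysis. The subset therefore gets signed-rank p-values and LS means, "including one-sided p-values as well as two-sided p-value and 95% CIs from the mixed-effects linear model". SAP 14.3.7 uses the subset again in two active T2 rows ("Tertiary (FAS for subset 'Baseline Period CUA count > 0"), one by Period and one by Visit.

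On the LS-mean margin, SAP 14.1.1 refers to the distribution of age, "EDSS categories at Baseline and respective Baseline Period CUA Lesion of the FAS". The opening of SAP Section 14 asks, where possible, for an "observed margin which reflects the population of the whole corresponding analysis set, regardless of missing data". The subset row names neither.

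Protocol 8.5.1 sets the status: "All analyses of all endpoints except the primary analysis, will be performed exploratively". The visible text nowhere mentions regression to the mean for this subset or limits how its p-values may be read.

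**The concern.** The subset is chosen on the quantity that is then subtracted. A subject at zero at baseline contributes a difference of zero or more, never less. Removing only such subjects pushes the mean and the signed ranks of the remainder below zero, whatever the drug does. This is regression to the mean produced by the selection rule.

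The result sits among the sensitivity analyses that are meant to show robustness of the primary finding. A reader may take a significant subset test, or a larger mean fall than in the FAS, as extra support for onset of action. With a single arm, nothing in the trial shows how much of that fall is selection. The exploratory label warns about chance and multiplicity; it does not warn of a bias that always favours the drug.

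**Working it through.** **Inputs from the documents.** One-sided 2.5%, fixed sequence H03, H02, H01, signed-rank with average ranks (SAP 14.1.1). CUA = mean T1 Gd+ per scan + active T2 without Gd+ per month (SAP 9). About 265 subjects (Protocol Synopsis). Baseline Period of at least 4 weeks and up to 3 months (Protocol 5.2).

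**Inputs assumed.** Lesion rates, their spread between subjects and the share with zero at baseline are not given.

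**Step 1: direction.** Let π0 be the share of subjects at zero, m0 their mean in the later period, and Δ the mean change in the subset. If rates are stable, the FAS mean change is 0, so

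(1 − π0)·Δ + π0·m0 = 0, hence Δ = −π0·m0 / (1 − π0).

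Δ is negative as soon as any zero-baseline subject has a later lesion.

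**Step 2: closed form for one model.** Take subject rates λ from a gamma distribution with mean μ and shape k, split equally between T1 per scan and T2 per month, with 2 scans and 3 months in both periods. The expected number of lesions at baseline is λ(0.5×2 + 0.5×3) = 2.5λ. Then π0 = (1 + 2.5μ/k)^(−k) and m0 = μ/(1 + 2.5μ/k).

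- μ = 0.5, k = 0.5: π0 = 3.5^(−0.5) = 0.535; m0 = 0.5/3.5 = 0.143; Δ = −0.0764/0.4655 = −0.164, on a subset baseline mean of 0.5/0.4655 = 1.074 (−15%).
- μ = 2, k = 0.5: π0 = 11^(−0.5) = 0.302; m0 = 2/11 = 0.182; Δ = −0.0548/0.698 = −0.08 on 2.86 (about −3%).
- μ = 4, k = 1: π0 = 1/11 = 0.091; m0 = 4/11 = 0.364; Δ = −0.0331/0.909 = −0.036 on 4.40 (about −1%).

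Simulation of the same model (4,000 runs each, N = 265) gave −0.164, −0.08 and −0.036.

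**Step 3: the plan's own level.** In that model, with no change in any subject's rate, the FAS test rejected in 2.2% to 2.8% of runs. With unequal period lengths and scan numbers it rejected in 0.9% to 3.1%. The 2.5% is reproduced for the FAS.

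**Step 4: the subset in the same runs.** Rejection was 78.6% for the first case above, 21.0% for the second and 6.0% for the third. With 80 subjects in total, the second case still gave 8.7%.

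**Step 5: a wider grid.** 2,000 replicates in each of 15 scenarios: gamma frailty variance 1, 2 or 3; T2 without Gd+ at half the T1 rate; screening-to-baseline interval uniform on 1 to 3 months; Periods 3, 2 and 1 with their own lengths and scan numbers. Baseline CUA was zero in 8% to 57% of subjects, and 20% to 52% of those rose in Period 3.

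| Mean T1 Gd+ per scan | Subset rejection, Period 3 | Mean change in subset |
|---|---|---|
| 0.5 | 61–90% | −10% to −16% |
| 1.0 | 35–44% | |
| 1.5 | 22–25% | about −3% |
| 2 | 13–18% | |
| 4 | 5–9% | about −1% |

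The FAS rejected in 2.0% to 3.2%. All three hypotheses fell in sequence in 3% to 87% of subset runs and 0.2% to 1.2% of FAS runs. With log-normal frailty, a 30% low-activity mixture or autocorrelated activity, the subset rejected in 5% to 95% and the FAS in 1.8% to 3.6%.

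**Step 6: the margin** (model adjusted for baseline CUA only). In the first case of Step 2, the null LS mean is −0.164 at the subset margin and +0.008 at the FAS margin. Over the grid, the 95% CI lay wholly below zero in 5% to 79% at the subset margin and in 0.6% to 2.6% at the FAS margin; nominal is 2.5%. The subset-margin CI covered the subset's own mean change in 92% to 95%. Under log-normal frailty the FAS-margin CI lay wholly below zero in 3% to 28%, so its near-nominal behaviour depends on the model.

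**Step 7: active T2** (equal, independent rates with and without Gd+ assumed). The Period 3 signed-rank test rejected in 3% to 20% of subset runs and 1.5% to 2.2% of FAS runs. In the by-Visit model at Months 2 and 3, the CI lay wholly below zero in 3% to 25% (subset margin) and 2% to 8% (FAS).

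**The case against.** The strongest reply is that nothing formal breaks. The subset has no confirmatory alpha, SAP 8.2 justifies it only by the floor effect, and the FAS result is reported whatever happens. This stands, and it limits the weight of the point.

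Second, the subset's change really is negative, so rejecting is correct for the observed change. The 2.5% fails only when the p-value is read as a drug effect. That is true, but a drug effect is what the primary objective is about. The FAS benchmark also assumes stable rates, while entry requires recent relapses; regression to the mean in the FAS itself was not examined.

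Third, 14.1.2 already cross-tabulates baseline CUA (zero or above, and in three classes) against each Period, and Section 14 plans descriptive statistics for subsets. These show how many zero-baseline subjects rise, and the mean change in the CUA = 0 subjects could be worked out by subtraction. They neither present that change nor qualify the subset p-values.

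Fourth, the size rests wholly on assumed inputs and is small in the mean at high rates. Some of the by-Visit T2 excess is also present in the FAS. Both are correct.

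Fifth, the specific margin rule in 14.1.1 could be held to override the general one, which applies only where possible. That reading is arguable but not stated, and 8.2 treats these groups as analysis sets. The same gap touches the other subgroup rows, and on its own it would be only a missing detail.

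Finally, part of the significance-level paragraph in SAP 9 is blacked out, so a caution there cannot be ruled out.

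**Conclusion.** The concern holds. Selection on the comparator biases the subset's change towards the drug in every scenario examined, and the direction follows from the definition whenever lesion rates are stable and some zero-baseline subjects later develop lesions. Read as evidence of a drug effect, the subset's signed-rank p-values do not hold 2.5%. The excess runs from mild (5% to 9% at a mean of 4 T1 Gd+ lesions per scan) to severe (61% to 90% at 0.5), conditional on assumed rates and spread.

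The margin is genuinely open. At the subset margin the LS mean carries the same artefact. At the FAS margin it is about unbiased in the base model but describes the FAS, not the subset. The confirmatory FAS sequence is untouched. This should be corrected, but it does not endanger the primary conclusion.

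**What to change.** In SAP 8.2 and 14.1.2:

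- Present the CUA > 0 subset descriptively, without hypothesis-test p-values and without any claim that it supports the primary result.
- Add a sentence saying that selection on the baseline count produces a fall by regression to the mean.
- State which LS-mean margin applies. Label any CI as describing the observed change in the subset (subset margin) or the FAS effect (FAS margin), not the drug effect in the subset.
- Show the change in the Baseline Period CUA = 0 subjects next to it.
- Put the same caution on the two active T2 rows for this subset in 14.3.7, where the effect is weaker.

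The cost is wording and one small extra output; no new data are needed. The sponsor gives up nominal p-values in an exploratory subset. SAP 6.2 indicates that the 6-month efficacy analyses have been run, so the change now concerns labelling and interpretation in the report. Any departure from the pre-specified display should be declared there.
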